**D. Subject Criteria (See Vulnerable Populations appendix, if applicable):**

Participants will be AA and white adult smokers  $\geq 21$  years old. The study will be open to both men and women. We have chosen to focus on AA because their unique smoking profile places them at potentially greater risk for tobacco-related disease and death and because AA smokers are understudied in terms of the potential differential effect of tobacco-related policy among this population.

Women who are pregnant, plan to become pregnant, or are breastfeeding will be excluded from the study because tobacco products will be provided and smoking is associated with low birth weight and premature labor. Children and those  $<21$  years old will be excluded because the minimum age for purchasing tobacco products is 21 years old.

1. Inclusion criteria: Non-Hispanic African American or white/Caucasian,  $\geq 21$  years old, smoke 5-30 cigarettes per day, daily cigarette smoker, smoked at current rate for at least 6 months, interested in trying e-cigarettes and HNB products, not interested in or unable/unwilling to quit cigarette smoking, willing to complete three in-person study visits, willing to have IV catheter placed.
2. Exclusion criteria: Interested in quitting cigarettes in the next 30 days, use of smoking cessation pharmacotherapy in the past 30 days, use of non-cigarette tobacco products in the past 30 days, use of e-cigarettes  $>5x$  in lifetime, use of e-cigarettes  $\geq 4$  of the past 30 days use of HNB products  $>5x$  in lifetime, use of HNB products  $\geq 4$  of the past 30 days, weight  $< 110$  lbs, uncontrolled hypertension (systolic BP  $\geq 180$  or diastolic BP  $\geq 105$ ), pregnant, plans to become pregnant, or breastfeeding, live  $>10$  miles from study site (Fairway CRU), current enrollment in a research study or program that aims to alter tobacco use.
3. Withdrawal/Termination criteria: Participants will be instructed to practice with (and attempt to switch to) each device prior to attending study visits 2 and 3. Participants may be removed from the study if they fail to complete

sufficient practice prior to each study visit. Additionally, participants will present to the lab nicotine deprived (12 hours abstinent) for study visits 1, 2, and 3. If participants present to study visit 1 and eCO is greater than 12 ppm or they report other nicotine use two times, they will be removed from the study.

4. Participants will not be allowed to participate in another research study that aims to alter their tobacco use during this research study.

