## **II. Research Plan and Design**

**A. Study Objectives:** The objective of this study is to understand the abuse liability and resultant toxicant exposure of new and emerging tobacco products in comparison to smokers' usual brand cigarette and to further understand how flavors in e-cigarette products impact abuse liability among menthol cigarette smokers. The current study is not a cessation study and does not aim to induce long-term uptake of the study products. The objective of the study is to test the acute pharmacokinetic profile and acceptability of these products during a 65-minute use period with each product across three to four study visits. African American and white smokers (N = 20) will be recruited and complete three to four in-laboratory sessions in a randomized crossover design.

**B. Study Type and Design:** The proposed study is a randomized crossover trial. Current smokers will be randomized to session order and complete a standardized 10-puff bout (5 minutes) followed by a 60-minute ad libitum session with each product (usual brand cigarette, e-cigarette, heat-not-burn). Throughout each visit, blood will be collected for nicotine analysis via an IV catheter placed in the patient's arm. Blood samples will be aliquoted into two separate vials. One will be analyzed for the current study and one will be placed in a biospecimen repository if participant provides consent for biorepository. Puff topography will be collected passively throughout the session to measure puffing patterns. Participants will complete self-report measures of nicotine withdrawal and craving. Finally, breath samples will be collected to measure changes in exhaled carbon monoxide, a potent lung toxicant, pre- and post-product use. At the final visit, participants will complete a behavioral economics concurrent choice task (see below for description) to behaviorally measure their decisions regarding use of e-cigarettes or HNB products in place of cigarettes. Finally, participants will be contacted by phone 6 months following the conclusion of visit 3 (or study discontinuation) to complete a phone survey. The objective of this survey is to assess for ongoing use of study products and is part of safety monitoring. We have no hypotheses related to the follow-up.

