**C. Sample size, statistical methods, and power calculation**

1. 20 eligible AA and white smokers will be randomized. We will use a 1:1 fashion randomization to product order (combustible cigarette, e-cigarette, heat-not-burn device vs. combustible cigarette, heat-not-burn device, e-cigarette). Randomization will be determined by computer-generated random numbers. Randomization assignments will be placed in sealed envelopes with sequential study ID numbers. After baseline data collection has been completed, the research assistant will select the sequential study ID number to determine the randomization assignment
2. No blinding is involved in the first three study visits. For participants who complete the fourth visit (flavor assessment), participants and research assistants that interact with participants will be blind to flavor (double blind design).
3. Due to the pilot nature of the current study, a primary aim of the study is to collect data for power calculations for a fully powered trial. Therefore, formal power calculations were not conducted. ANOVAs will be conducted to detect within-subject differences between products for all outcomes. A Bonferroni correction will be applied to adjust for multiple comparisons. A paired samples t-test will be conducted to detect differences in outcomes in the e-cigarette flavor assessment.

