- c. **Between visits one and two:** Participants will be provided with the product to be used at the next visit (determined by randomization completed at the end of visit one) and asked to take it home for 48 hours (+3 days) and instructed to, at minimum, practice using it 2-3 times per day between visits. However, they will be encouraged to full substitute the study product for their cigarettes to ensure they conduct sufficient practice. They will be provided with e-liquid or heat sticks and the device for practice. Participants will complete and return a practice log at the following visit.
- d. **Visit two:** Aside from the product being used, visit two will closely mirror visit one. Participants will complete baseline self-report measures regarding their practice period (product liking/evaluation and preferences). Participants will again complete CO measurement to confirm tobacco/nicotine abstinence. They will complete a PK and ad-lib session identical to visit one. At the end of the session, they will be oriented to the final device and again instructed to practice with (and attempt to fully substitute) it at home. Participants will be compensated \$75 for this visit. We anticipate the visit to last no more than 2.5 hours.
- e. **Between visits two and three:** Participants will be provided with the product to be used at the next visit (determined by randomization completed at the end of visit one) and asked to take it home for 48 hours (+3 days) and instructed to, at minimum, practice using it 2-3 times per day between visits. However, they will be encouraged to full substitute the study product for their cigarettes to ensure they conduct sufficient practice. They will be provided with e-liquid or heat sticks and the device for practice. Participants will complete and return a practice log at the following visit.

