**C. Informed consent process and timing of obtaining of consent**

- 1 Consent procedures will be conducted by trained members of the research team. Prior to consent, participants will be provided a detailed and comprehensive overview of study procedures.
- 2 Individuals interested in the proposed study will meet the research assistant at the Fairway CRU. Each individual will be given a copy of the consent form and as much time as they need to review its contents. After the consent form is read, both the individual and the research assistant will review the consent form together and the potential participant will be encouraged to ask questions. Each individual will be reminded that participation in the study is completely voluntary. The consenting process will take place in a private location.
- 3 We are recruiting otherwise healthy smokers and do not anticipate recruitment of subjects with compromised cognitive abilities and/or decisional impairment. However, if questions regarding a participant's ability to provide informed consent arise, Drs. [name] and [name] will determine whether the subject is able to give informed consent.

**D. Alternatives to Participation:** The alternative to participation is not participating.

**E. Costs to Subjects:** There are no costs to participants. All tests, procedures, and visits are being performed solely for research purposes and are not billable to insurance companies.

**F. How new information will be conveyed to the study subject and how it will be documented:** We have plans to publish data from this study in aggregate but will not provide any individualized feedback to patients.

**G. Payment, including a prorated plan for payment:** Participants who screen fail at visit one will be compensated \$20 and will not be allowed to continue with the study. Eligible participants who complete study procedures will receive \$50 for visit one, \$75 for visit two, \$100 for visit three, and \$50 for visit four (if

participant qualifies) in appreciation for their time and participation. Participants may receive an addition \$50 at visit three if they attend all visits, return completed practice logs, and have CO  $\leq$  12 ppm at all visits. For each visit that must be rescheduled due to CO  $>$  12 ppm or an incomplete practice log, participants will have \$10 deducted from their bonus. Finally, participants will be provided transportation via a rideshare service to and from each visit.

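### Removal for undefined insufficient practice follows randomisation, is not reconciled with the rescheduling rule, and can select the device data toward practised or willing users

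*Combined protocol and SAP*

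**What the plan says.** Section II.E.2.b places randomisation to device order at the end of visit 1, after the usual-brand cigarette session. Home practice with the assigned device follows. Under II.E.2.c and II.E.2.e participants are "instructed to, at minimum, practice using it 2-3 times per day between visits", are encouraged to substitute fully, and return a log.

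Three places then bear on someone who practises little:

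- **II.D.3 (withdrawal/termination):** "Participants may be removed from the study if they fail to complete" sufficient practice. The threshold is not defined, no decision-maker is named, and there is no link to the 2-3 times per day in II.E.2.
- **III.G (payment):** the sentence that opens "For each visit that must be rescheduled due to CO" also covers visits rescheduled for an incomplete practice log, and takes $10 from the $50 bonus each time.
- **II.C.2:** the first three visits are not blinded.

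The stated purpose includes acceptability: "The objective of the study is to test the acute pharmacokinetic profile and acceptability of these products during a 65-minute use period". Section V.B names nicotine delivery as the primary endpoint. On analysis, II.C.3 says "ANOVAs will be conducted to detect within-subject differences between products for all outcomes" and "A Bonferroni correction will be applied to adjust for multiple comparisons". Neither II.C nor V.A gives an analysis set, a missing-data method, a replacement rule or a plan to report removals.

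**The concern.** Removal here is a discretionary exclusion after randomisation, made when the device is known, on a variable that the protocol itself connects with the primary endpoint. Section I.B.2 says that some smokers draw nicotine from the JUUL effectively while others may need considerable practice to reach cigarette-like levels.

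The exclusion is also lopsided. The cigarette session is finished before any practice begins, so only device sessions can be lost. Removal before visit 2 loses both devices, even though only one was practised. Removal before visit 3 loses the second device and the choice task. The only later contact described is the six-month safety call (II.E.2.h).

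Device-versus-cigarette results could then describe people judged to have practised enough, while being read as results for smokers who try these products. Because II.C.3 makes data for a later power calculation a primary aim, selected means and SDs would carry into the next trial's design.

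**Working it through.** **Plan's own figure.** The plan states "20 eligible AA and white smokers will be randomized" and then "Therefore, formal power calculations were not conducted". It gives no effect size, SD, alpha or power, so 20 cannot be reproduced. What follows is a sensitivity calculation on assumed inputs.

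**Inputs**
- N = 20 (II.C.1).
- Fraction removed, q: not given. Assumed 1, 2, 4 or 6 of 20.
- Correlation ρ between practice and the within-person device-minus-cigarette difference: not given. Assumed -0.3 to 0.7.
- Alpha and number of comparisons: not given. Assumed 0.05, and 0.05/3 for three pairwise comparisons.

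**Shift in the mean.** Suppose practice and the difference are bivariate normal and the lowest fraction q on practice is removed. The mean difference among those left moves by ρ × λ, with λ = φ(z_q)/(1 - q), in SDs of the difference. For q = 0.10, λ = 0.1755/0.90 = 0.195. For q = 0.30, λ = 0.3477/0.70 = 0.497. The standard error is 1/√n in the same units.

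| Removed | λ | ρ = -0.3 | ρ = 0 | ρ = 0.3 | ρ = 0.5 | ρ = 0.7 | SE |
|---|---|---|---|---|---|---|---|
| 1 of 20 | 0.1086 | -0.033 | 0 | 0.033 | 0.054 | 0.076 | 0.229 (n = 19) |
| 2 of 20 | 0.195 | -0.058 | 0 | 0.058 | 0.097 | 0.136 | 0.236 (n = 18) |
| 4 of 20 | 0.350 | -0.105 | 0 | 0.105 | 0.175 | 0.245 | 0.250 (n = 16) |
| 6 of 20 | 0.497 | -0.149 | 0 | 0.149 | 0.248 | 0.348 | 0.267 (n = 14) |

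Against the standard error:
- Two removals at ρ = 0.5: 0.097/0.236 = 0.41 SE.
- Two removals at ρ = 0.7: 0.136/0.236 = 0.58 SE.
- Six removals at ρ = 0.7: 0.348/0.267 = 1.30 SE.

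**Check by simulation** (20,000 runs, 4 of 20 removed, true mean difference zero, nominal two-sided 5% test). At ρ = 0.3 / 0.5 / 0.7 the shifts were 0.10 / 0.17 / 0.24, close to the formula. False-positive rates were 6.9% / 11.3% / 18.0%, against 5.3% at ρ = 0.

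**Precision, if only complete cases are analysed.** The paired effect detectable with 80% power (noncentral t) rises from 0.66 SD at n = 20 to 0.75 SD at n = 16 for alpha 0.05, and from 0.78 to 0.90 SD for 0.05/3. The rule can act before visit 2 and again before visit 3. Removing 10% each time leaves 20 × 0.9 × 0.9 = 16.2 participants.

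**The case against.** **Practice is deliberate.** Participants are daily smokers with at most five lifetime uses of each device type (II.D), so they come practised with cigarettes and new to the devices. Practice reduces that imbalance, and delivery in practised users is a legitimate target. This stands as a reason for the practice period. But the plan never states that target, and it would not answer the acceptability question.

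**Removals may be few.** Entrants must be interested in trying both products, practice is brief, logs count toward a bonus and visits can be rescheduled. This stands: with one or two removals the shift is below the noise of a 20-person pilot.

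**The shift may be conservative.** Aim 1 expects cigarettes to show the greatest delivery, topography and craving relief, so a shift toward the devices works against H1 to H3. This stands for cigarette-versus-device contrasts. H1 and H2 also rank the e-cigarette above the heat-not-burn device, and there the direction is open.

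**Three stronger readings that the documents do not support**
- A reader might infer that those removed dislike the device and that the bias always favours the devices. The documents do not say why people under-practise. The shift vanishes at ρ = 0 and reverses at negative ρ. Direction may also differ by outcome: practised users may puff more, which could raise exhaled CO from the heat-not-burn device.
- A reader might call II.D.3 and III.G contradictory. II.D.3 is permissive, and an incomplete log is not the same as too little practice, so both can operate. They are unreconciled.
- A reader might assume that the ANOVA discards a removed person's cigarette session. That holds for a complete-case analysis, but the plan gives no rule for incomplete cases.

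**Conclusion.** The point holds in a limited form. The plan permits removal after randomisation, under open-label conditions and on an undefined threshold, for a variable that it ties to e-cigarette nicotine delivery. Only device sessions can be lost, and no analysis rule covers the loss. If practice correlates positively with device outcomes, device nicotine delivery and acceptability relative to cigarettes would be overstated, by about 0.06 to 0.35 SD for 2 to 6 removals and correlations of 0.3 to 0.7. Those inputs are assumptions, as is removal strictly from the lowest practice upward; the documents fix neither the size nor the sign. The point is worth acting on because the remedy is cheap and serves both the all-user and the practised-user question, not because a large bias has been shown.

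**What to change.** 1. Reconcile II.D.3, II.E.2.c/e and III.G: define sufficient practice, name who decides, and state which consequence applies when, so that low practice alone does not lead to loss of outcome data. Which withdrawal or rescheduling rule to adopt is for the study team.
2. Record the practice count from the log for each device.
3. In II.C and V.A, define the analysis set as all randomised participants with any session, analysed in a mixed model rather than a complete-case within-subject ANOVA. The model keeps the sessions that exist but cannot recover those never held, so step 1 matters most.
4. Add a sensitivity analysis limited to device sessions that met the 2-3 times per day minimum.
5. Report removals by device and by order.

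The cost is a short amendment and one extra analysis. The downside is that sessions by less-practised users may add variance and lower mean e-cigarette nicotine delivery; comparing the main and practised-sessions results would show by how much.

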#### **A. E. Specific methods and techniques used throughout the study**

1. Laboratory tests: Throughout each visit, blood will be collected for nicotine analysis via an IV catheter placed in the patient's arm. Blood draws will occur during the PK phase of each visit and will be taken at baseline (0 minutes), 5 minutes, 7 minutes, 15 minutes, and post-ad lib portion (may vary by participant depending on how long they choose to use the product). No more than 7 mL of blood will be drawn per draw ( $\leq 35$  mL per visit). Blood will be processed and analyzed for nicotine and cotinine levels. If consent is provided for banking, samples will be banked for possible future analysis.
2. Study Procedures:
  - a. **Initial screening:** The initial screening will review inclusion/exclusion criteria. Those eligible will be scheduled to completely visit within 14 days.
  - b. **Visit one:** At visit one, participants will be re-screened according to inclusion/exclusion criteria. They will be instructed to remain nicotine abstinent for 12 hours prior to the visit. Participants will complete carbon monoxide (CO) measurement to confirm abstinence ( $CO \leq 12$  ppm). CO is collected by a simple, non-invasive breath test that involves the participant holding their breath for  $\sim 15$  seconds and then exhaling into a straw connected to the CO monitor. Participants will be provided with an overview of the study, will provide informed consent, and complete baseline self-report measures. Participants will then complete the PK phase of the study. Participants will have an intravenous catheter placed in their arm. They will complete a 10-puff standardized puffing bout followed by a 60-minute ad-lib smoking session with their usual brand cigarette. Specifically, a research assistant with a stopwatch will instruct the participant to take a puff every 30 seconds, resulting in 10 puffs over 5 minutes. Throughout the session, puff topography will be measured via a pressure sensor attached to the device/product. This will not require anything additional of the participant. Blood draws will occur during the 10-puff bout at -5, 5, 7, 15, and at the end of the ad-lib smoking period ( $\sim 60$  minutes after the 10-puff bout). Following the smoking period, the participant will be instructed to make notes regarding their preferences related to the product (e.g., liking, satisfaction, craving, intentions/willingness for future use). Participants will complete self-report measures of nicotine craving and withdrawal at each blood draw during the 10-puff bout and every 10 minutes throughout the ad-lib smoking period. At the end of the session, participants will complete a measure of product liking/evaluation. At the end of visit one, participants will be randomized to product order (e-cigarettes followed by HNB device vs. HNB device followed by e-cigarette). Participants will be shown how to use the device, puff on it, charge it, replace the pod/heat stick. Participants will be compensated \$50 for this visit.

[figure not shown]
addition, participants will be asked to bring an unopened pack of their usual brand cigarettes to this visit. They will be compensated an additional \$6 for this, bringing their total compensation to \$56 for this visit. We anticipate the visit to last no more than 3 hours.

- c. **Between visits one and two:** Participants will be provided with the product to be used at the next visit (determined by randomization completed at the end of visit one) and asked to take it home for 48 hours (+3 days) and instructed to, at minimum, practice using it 2-3 times per day between visits. However, they will be encouraged to full substitute the study product for their cigarettes to ensure they conduct sufficient practice. They will be provided with e-liquid or heat sticks and the device for practice. Participants will complete and return a practice log at the following visit.
- d. **Visit two:** Aside from the product being used, visit two will closely mirror visit one. Participants will complete baseline self-report measures regarding their practice period (product liking/evaluation and preferences). Participants will again complete CO measurement to confirm tobacco/nicotine abstinence. They will complete a PK and ad-lib session identical to visit one. At the end of the session, they will be oriented to the final device and again instructed to practice with (and attempt to fully substitute) it at home. Participants will be compensated \$75 for this visit. We anticipate the visit to last no more than 2.5 hours.
- e. **Between visits two and three:** Participants will be provided with the product to be used at the next visit (determined by randomization completed at the end of visit one) and asked to take it home for 48 hours (+3 days) and instructed to, at minimum, practice using it 2-3 times per day between visits. However, they will be encouraged to full substitute the study product for their cigarettes to ensure they conduct sufficient practice. They will be provided with e-liquid or heat sticks and the device for practice. Participants will complete and return a practice log at the following visit.
- f. **Visit three:** Aside from the product being used, the first portion of visit three will closely mirror visits one and two. Participants will complete baseline self-report measures regarding their practice period (product liking/evaluation and preferences). Participants will again complete CO measurement to confirm tobacco/nicotine abstinence. They will complete a PK and ad-lib session identical to visits one and two. Following the PK and ad-lib sessions, participants will have a 1.5-hour washout/rest period in order to bring them to a state of nicotine deprivation. During the washout period, participants will be allowed to watch a movie or listen to music. Participants will then complete a concurrent choice task with their usual brand cigarette, e-cigarette, and HNB device. In the task, participants will earn puffs of the various products by clicking a mouse/keyboard a set number of times. The participants will be free to choose how they allocate the puffs between the available products. For each task, participants can earn up to 20 puffs and the task will last up to 1.5 hours. Puff topography will be measured throughout the task. The objective of the task is to behaviorally measure whether or not participants see the e-cigarette and/or HNB device as an acceptable or preferable substitute for their usual brand cigarette. Participants will be compensated \$100 for visit

three. In addition, participants will earn up to \$50 for completing all study visits (see section III.G.). We anticipate that visit three will last no more than 4.5 hours.

i. **Computer task:** The usual brand cigarette, e-cigarette, and HNB product are all available. Participants will earn puffs of the products by clicking boxes on a computer screen that represent the products. To earn 1 puff of a product, the participant will be instructed that they must click the corresponding box. In order to earn puffs of the e-cigarette or HNB product, they will click the corresponding box 10 times. To test relative demand for their usual brand cigarette, it will be placed on a variable ratio, meaning the number of clicks necessary to earn puffs of the usual brand cigarette will increase with each trial of the task. Once participants earn a puff, they will be given two minutes to have the puff before the next trial begins.

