Aim 2: Examine resultant toxicant exposure of heat-not-burn devices, e-cigarettes, and combustible cigarettes. H1: Exhaled carbon monoxide will be greatest for cigarettes, followed, by heat-not-burn devices and e-cigarettes (no exposure).

**Aim 3:** Understand the comparative acceptability of tobacco and menthol flavored e-cigarettes among menthol cigarette smokers. H1: Menthol cigarette smokers will show increased topography measures when using the menthol (vs. tobacco) flavored e-cigarette. H2: Menthol cigarette smokers will show increased acceptability and more positive subjective effects when using the menthol (vs. tobacco) flavored e-cigarette.

**Exploratory Aim:** Understand differences in abuse liability of e-cigarettes, HNB products, and cigarettes as measured behaviorally in a concurrent choice task.

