#### **V. Data Analysis and Reporting**

**A. Statistical and Data Analysis:** See section II.C. above for sample size and power calculations. To determine differences on self-report measures between products, an analysis of variance (ANOVA) will be conducted. Differences in nicotine delivery will be compared across products at each timepoint using similar procedures. Mean differences in puff allocation will be investigated for the computer task.

**B. Outcome:** The primary study endpoint is nicotine delivery. We hypothesize that combustible cigarettes will show the fastest and greatest nicotine delivery, followed by e-cigarettes, and heat-not-burn devices. Further, topography measures will be greatest for cigarettes, followed by e-cigarettes, and heat-not-burn devices. In terms of self report measures of abuse liability, use of cigarettes will be associated with the greatest reduction in symptoms of nicotine withdrawal and craving. Exhaled carbon monoxide will be greatest for cigarettes, followed by heat-not-burn devices and e-cigarettes (no exposure). The primary endpoint of the computerized concurrent choice task is the proportion of puffs allocated to each product. The third aim is exploratory, and we therefore do not have specific hypotheses related to aim three.

**C. Study results to participants:** Study results will not be shared with research participants.

**D. Publication Plan:** We plan to publish results in appropriate tobacco and public health journals such as Addiction, Tobacco Control, Nicotine and Tobacco Research, etc. In addition, results will be presented at regional, national, and international conferences.

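### CO, the only abstinence check named at visits 2 and 3, cannot by the plan's own hypothesis show e-cigarette use, and the assayed pre-use nicotine has no role in an undefined primary endpoint

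*Combined protocol and SAP*

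**What the plan says.** - **Requirement.** II.D.3: "participants will present to the lab nicotine deprived (12 hours abstinent) for study visits 1, 2, and 3".
- **Check.** II.E.2.d, repeated in II.E.2.f: "Participants will again complete CO measurement to confirm tobacco/nicotine abstinence". The 12 ppm limit is given in II.E.2.b, in the timeline note (II.E.6) and in the payment rule (III.G).
- **What CO is expected to show.** Aim 2: "Exhaled carbon monoxide will be greatest for cigarettes, followed, by heat-not-burn devices and e-cigarettes (no exposure". V.B repeats it: "Exhaled carbon monoxide will be greatest for cigarettes, followed by heat-not-burn devices and e-cigarettes (no exposure".
- **Home use.** Before visits 2 and 3 the participant keeps the next device for 48 hours (+3 days), and "they will be encouraged to full substitute the study product for their cigarettes to ensure they conduct sufficient practice" (II.E.2.c and e). "Participants will complete and return a practice log at the following visit", but the log is given no abstinence role.
- **Self-report.** Other nicotine use appears in one removal sentence of II.D.3, "If participants present to study visit 1 and eCO is greater than 12 ppm or they report other nicotine use two times", which is tied at least partly to visit 1.
- **Order.** Both sequences in II.C.1 start with the cigarette. Only the order of the two devices is randomised, at the end of visit 1 (II.E.2.b).
- **Blood.** II.E.1: draws "will be taken at baseline (0 minutes), 5 minutes, 7 minutes, 15 minutes, and post-ad lib portion", assayed for nicotine and cotinine. II.E.2.b times the pre-use draw at -5 minutes.
- **Analysis.** II.C.3 gives within-subject ANOVAs with Bonferroni correction. V.A compares nicotine delivery between products timepoint by timepoint. V.B makes nicotine delivery the primary endpoint. None of them says whether it is a level or a change, and none includes a baseline term. The background (I.B.2) speaks of both a boost and levels.

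**The concern.** A check is said to confirm nicotine abstinence when, on the plan's own premise, it is blind to one of the two products issued for home use. Participants are told both to practise with the device, ideally in place of cigarettes, and to stop 12 hours before the visit, so some late use is plausible. It could occur only once a device has been issued, that is, before visits 2 and 3 and never before the cigarette session. The contrast exposed is therefore device against cigarette, which is the first hypothesis of Aim 1.

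The measurement that would reveal the problem is already collected but has no stated use. Two analysts could follow V.A faithfully, one comparing levels and the other changes, and report different primary results. If pre-use nicotine differed between products, their errors would point in opposite directions. The pilot's estimates are also meant to inform the power calculation for a larger trial (II.C.3).

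**Working it through.** The documents give no figure to reproduce: no rate of non-abstinence, nicotine elevation, half-life or expected product difference. Only N = 20 (II.C.1) and the draw times (II.E.1, II.E.2.b) come from the plan. Every other input below is assumed and serves only to show how level and change behave.

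**1. Pre-use shift at a device visit** = share of participants x elevation.
- Share 0.10-0.50, elevation 2-8 ng/mL: 0.10 x 2 = 0.2 up to 0.50 x 8 = 4.0 ng/mL. With full compliance it is 0.
- If 10-25% also smoked undetected before visit 1 (2-8 ng/mL), the net device-minus-cigarette shift runs from 0.10 x 2 - 0.25 x 8 = -1.8 to 0.50 x 8 - 0.10 x 2 = +3.8. The sign is open.

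**2. Carry-through to later draws.** With the pre-use draw at -5 minutes, the fraction left at minute t for half-life h is f = 2^(-(t+5)/h). Bias of a level = shift x f. Bias of a change = shift x (f - 1). At the top of the range (shift 4.0):

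| Draw | f at h = 60 / 120 / 180 min | Level | Change |
|---|---|---|---|
| 5 min | 0.891 / 0.944 / 0.962 | +3.56 / +3.78 / +3.85 | -0.44 / -0.22 / -0.15 |
| 15 min | 0.794 / 0.891 / 0.926 | +3.17 / +3.56 / +3.70 | -0.83 / -0.44 / -0.30 |
| End of ad lib (about 65 min) | 0.445 / 0.667 / 0.764 | +1.78 / +2.67 / +3.05 | -2.22 / -1.33 / -0.95 |

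At the early draws, change removes most of the shift. At the last draw, change has the larger absolute error only when f < 0.5, that is h < 70 min (h < 65 min if the baseline draw is at 0).

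**3. Pre-use nicotine as a covariate.** In simulations with N = 20, three sessions, participant effects and the decay of step 2, the covariate model left -0.04 to +0.04 ng/mL at the 5-minute and last draws. This is largely built in, because the data were generated in the form that the model fits. With 1 ng/mL of noise in the pre-use value up to 0.28 remains, and with 2 ng/mL up to 0.93.

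**4. Prior use that lowers ad-lib intake for one device.** Take h = 120, the last draw, both devices elevated, and e-cigarette intake lowered by 0.6 per ng/mL of pre-use nicotine. The slope is 0.667 - 0.6 = 0.067 for the e-cigarette and 0.667 for the other device. The pooled covariate slope is then about (0.067 + 0.667)/2 = 0.367. Bias in e-cigarette minus cigarette:

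| Shift | Level | Covariate, approximate | Change |
|---|---|---|---|
| 0.25 x 5 = 1.25 | 1.25 x 0.067 = +0.08 | 1.25 x (0.067 - 0.367) = -0.38 | 0.08 - 1.25 = -1.17 |
| 0.50 x 8 = 4.0 | 4.0 x 0.067 = +0.27 | 4.0 x (0.067 - 0.367) = -1.20 | 0.27 - 4.0 = -3.73 |

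Simulation gives about -0.4 and -1.2 for the covariate model. If the other device is the one affected, the covariate bias turns positive (+0.33 and +1.15), against +0.85 and +2.67 for the level. No method is best throughout at the last draw.

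**The case against.** The plan has safeguards. Twelve-hour abstinence is required, and visits 2 and 3 are said to mirror visit 1 closely, so staff may well ask about nicotine use. A practice log is returned. CO still covers smoking, the established habit of these participants, who have used e-cigarettes at most five times. Above all, pre-use nicotine is assayed, and a timepoint-by-timepoint comparison that includes the baseline draw would show an imbalance. The sizes are all assumed, and this is a pilot of 20 with no power claim.

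Most of this stands and limits the point. It does not remove it: neither mirroring nor the log is named as an abstinence check, and a visible pre-use imbalance would still have no handling rule.

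A reader might infer more than the documents support:
- **That the primary comparison is biased towards the devices.** No rate or size is given, smoking before visit 1 would act the other way, and the net range in step 1 spans zero.
- **That CO also misses heat-not-burn use.** The hypothesis places that product between cigarettes and e-cigarettes. Its CO sensitivity is not stated.
- **That covariate adjustment is proven superior, or that subtraction is wrong at the last draw.** Step 4 shows the covariate model doing worse than the raw level. Step 2 shows subtraction losing to the raw level only below an assumed 70-minute half-life.

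**Conclusion.** The point holds on the text. The check named at visits 2 and 3 cannot do all that is claimed for it, undetected device use can fall only on device sessions, and the analysis neither defines nicotine delivery nor uses the assayed pre-use value. This should be fixed, with medium confidence in its practical importance.

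The 0.2-4.0 ng/mL shift and everything derived from it are illustrations from assumed inputs. What they establish is that, when pre-use nicotine is unbalanced, level and change err in opposite directions, so the choice has to be made in advance. For the 5, 7 and 15 minute draws, which II.E.2.b groups with the fixed 10-puff bout, accounting for baseline is well supported under the assumed decay. For the end-of-ad-lib draw no single approach is established as best.

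**What to change.** In V.A:
1. Define nicotine delivery at named draws as a measure that accounts for that visit's pre-use nicotine. For the 5, 7 and 15 minute draws, use a within-subject model with pre-use nicotine as covariate, or change from the pre-use draw. For the end-of-ad-lib draw, pre-specify one approach and report the unadjusted level beside it, because adjustment and subtraction can both mislead if prior use alters ad-lib intake.
2. Report pre-use nicotine by product.
3. Pre-specify a supportive sensitivity analysis that excludes sessions whose pre-use nicotine exceeds a limit fixed before the nicotine data are seen.

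In II.E: describe CO of 12 ppm or less as a check on smoking abstinence only, and reconcile the 0 and -5 minute labels of the pre-use draw. No change to the abstinence, rescheduling or removal rules is proposed.

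**Cost.** Wording and slightly more analysis; the blood is already drawn and assayed. In the assumed scenarios the covariate model's standard error was at worst about 1.1-1.2 times that of the raw level, and in some it was smaller. For change with equal variances the ratio is sqrt(2(1 - rho)): 1.18, 1.00 and 0.77 at rho = 0.3, 0.5 and 0.7, and 1.41 at rho = 0. If 10-50% of sessions for a device are excluded, 18 to 10 of 20 pairs remain. The 95% interval half-width, in SD units t/sqrt(n), goes from 0.468 (n = 20) to 0.497 (n = 18) or 0.715 (n = 10), that is 1.06 to 1.53 times as wide. The exclusion is not random, so that analysis can only be supportive.
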